TRADITIONAL MONGOLIAN SWADDLING AND DEVELOPMENTAL DYSPLASIA OF THE HIP: A RANDOMIZED CONTROLLED TRIAL

RESEARCH PROTOCOL

[name] and SMOPP team
National Center for Maternal and Child Health, Mongolia
29 June, 2019

SUMMARY

Background

In Mongolia, swaddling is an ancient practice and nowadays it still remains common child care in the first months of life. Mongolian traditional way of swaddling technique involves tight, prolonged wrapping from the head or neck down in two to three layers of thin cotton cloth, covered by layers of thick blankets and binding with 2-3 tiers for whole day. This traditional prolonged swaddling where arms and legs are extended and hips are in adduction position might increase the risk for developmental dysplasia of the hip (DDH). DDH is a major health problem that can lead to lifelong disability if diagnosis is missed in first weeks of life. Mongolia is the first Asian country that launched a universal ultrasound hip screening (Graf's method) for DDH in newborns. All DDH cases are followed up on monthly basis by hip ultrasound and treated with a simple extension and abduction orthosis if necessary.

Objectives

To test the effect of traditional swaddling on the DDH in Mongolia

Design

A prospective, randomized trial with two study groups will be conducted in Mongolia. The term newborns with Graf Type 2a (physiologically immature) will be randomly allocated to one of two groups. The intervention/"non-swaddling" group will be instructed not to swaddle at all. The control/"swaddling group" will be swaddled in the common traditional Mongolian method. Both groups will be followed up by Graf's method of hip ultrasound at 4-6 weeks' intervals until healing according to Mongolian national guideline. All infants in need of therapy (Graf type 2a-, 2c or worse) will be treated with Tubinger orthosis. At around 12 months of age all children will be checked again by Graf's method of hip ultrasound.

Timeline and Analysis

The study will be conducted between August 2019-March 2021. Findings will be reported in March-June 2021. Analysis will be intention to treat.

Ethics

The study protocol will be reviewed and approved by the Institutional Review Board at the National Center for Maternal and Child Health and the Ethical Review Committee of Ministry of Health, Mongolia prior to start the study.

1. BACKGROUND AND JUSTIFICATION

Developmental dysplasia of the hip (DDH) belongs to the most common disorders of osteoarticular system with public health priorities in generally otherwise healthy infants. Severity can range from a minor acetabular dysplasia to a complete dislocation. Estimates of the incidence of DDH are quite variable and depend on detection methods, ages of the child, and diagnostic criteria etc.¹⁻⁸ A Mongolian study reported that the nationwide hip ultrasound screening by Graf method detected 14.6% of physiologically immature and 1.2% of dysplastic cases.⁹ Another prospective study reported 1.3% incidence of DDH by Graf method of ultrasound.¹⁰ DDH is a multifactorial disorder that genetic and non-genetic factors are involved in its etiology. Contributing factors for the development of DDH are space (big infants), position in utero and hormonal factors (Relaxin) and genetic predisposition.¹¹ In addition, postnatal mechanical factors are also important but not studied thoroughly yet.¹²

Fetal hip joint consists of cartilaginous tissue on a osseous basis. During further maturation, the cartilage is subsequently replaced by bone. Studies have shown that hip joints have a considerable potential for maturation even after birth i.e during the first weeks of life.^{13,14} These unique features allow detect by ultrasound and treat DDH conservatively during this window of opportunity. The early detection and simple treatment with an extension and abduction orthosis in the first weeks of life mostly leads to a maturation and cure of the hip joints, and subsequently, prevents handicaps in children later in life. However, there is still continuing discussion about whether to screen for DDH.^{2,15,16} One point of contention is whether hip joints below the threshold of 60° alpha should be classified as pathological (DDH) or whether a range of physiological immaturity (Graf types 2a / 2a+) is defined where a wait-and-control approach is chosen.^{2,15,17} However, these hips may be vulnerable to persistent dysplasia if postnatal mechanical factors such as swaddling are used in child care. Some studies have found that a history of swaddling to be one of the risk factors for DDH.¹⁸⁻²⁰ Also the swaddling history was more common in late presenting infants with hip dislocation.²¹

In many cultures around the world newborn babies are swaddled to calm them down and fall asleep, and some cultures believe that swaddling can prevent the baby from suffering cold weather especially during winter time. In Mongolia, swaddling is an ancient practice and nowadays it still remains common child care in the first months of life. Mongolian traditional way of swaddling technique involves tight, prolonged wrapping from the head or neck down in two to three layers of thin cotton cloth, covered by layers of thick blankets and binding with 2-3 tiers. However, this prolonged swaddling in the first year of life did not have any significant impact on children's early mental or psychomotor development.²²

In Mongolia, the Graf's method of hip ultrasound was introduced in 2007 by Swiss-Mongolian Pediatric Project (SMOPP), a private/non-governmental humanitarian aid project, and has subsequently become step by step a nationwide screening program. Trained neonatologists or pediatricians of Maternity hospitals screen all newborns using the Graf's method²³ of hip ultrasound and perform a flexion-abduction treatment, if necessary. The routine guideline is the following: newborns with Type 1 hips are discharged without any further follow-up. Newborns with Type 2a hips are followed up by ultrasound in monthly intervals until these mature. Children who have 2a hips during the course of follow-up are either followed up (Type 2a+), or treated if the hip insufficiently matured (Type 2a-). Children with Type 2c to 4 hips are treated with a Tübingen hip extension and abduction orthosis and also followed up until fully mature. Children

with Type 4 hips that could not be splinted are referred for surgical interventions.²² Full documentations of all cases is mandatory.

Recent studies in Mongolia showed that 10-15% of newborns have physiological immaturity (Type 2a hip by Graf method) at birth.⁸ Given the high prevalence of traditional swaddling in the country, any association with DDH could have large public health implications. We will investigate the effect of traditional tight and prolonged swaddling on DDH in Mongolia in this prospective randomized controlled trial (RCT).

2. OBJECTIVES

Mongolian traditional prolonged swaddling where arms and legs are extended and hips are in adduction position increases the risk for DDH. This hypothesis is going to be tested in this study.

The primary outcomes: The number of “non-Type 1” hip cases at the monthly follow-up ultrasound control visits

The secondary outcomes:

- a. number of DDH cases (Graf Type 2a-, Type C, D and Type 4) at any monthly follow-up ultrasound control visits and rim defects at 12 months’ follow-up
- b. correlation between the primary outcome and the swaddling frequency (in hours per day) and swaddling duration (in days)
- c. primary and secondary outcomes association with the swaddling.

3. STUDY METHODOLOGY

3.1. Study design

A prospective interventional randomized controlled trial with two study groups will be conducted in Mongolia.

“Swaddling” group: The newborns randomized into the “swaddling” group will be swaddled in the common traditional Mongolian method at least 20-24 hours every day for 4-6 weeks. Traditional swaddling in Mongolia is as follows: Swaddling is a tightly wrapping (2 adult fingers pass under the cloth) of a baby in several layers of cloth, covered by one warmer blanket from head and neck to toe in a straight position after birth for day and night time. Two or three ropes are used across a baby's body for binding to avoid unwrapping. Since the non-swaddling clothes have to be provided with alternatives to the readily available swaddling clothes and blankets, the swaddled group will be given a blanket and several cotton sheets at the time of recruitment.

“Non-swaddling” group: The “non-swaddling” group will be instructed not to swaddle at all for 4-6 weeks. The required size and warmth of clothing required to keep a newborn infant warmly clothed will be provided to the family. Also, wide warm sleeping bags that allow free legs movements will be provided to prevent swaddling when go outdoors.

3.2. Sampling and randomization

Study site: The National Center for Maternal and Child Health (NCMCH) is purposely selected as a study site. Approximately 50% of all deliveries in Ulaanbaatar occur in the center and there are about 11,000 live births annually. As the center is a specialized tertiary care level teaching hospital, it is responsible for providing services for follow-up ultrasound controls and treatment of DDH cases in Ulaanbaatar. There are two term-delivery units with 6 neonatologists/screeners, a preterm-

delivery unit with 6 neonatologists/screeners and a pediatric radiology unit with 6 radiologists. Data will be collected from September 2019 to March 2021.

Sample size calculations: The primary outcome of interest is dichotomous (Graf Type 1 or non-Type 1 hips). If we assume that 10% of the subjects on the non-swaddled group has a non-Type 1 hip and it is of clinical relevance only if we observe a 30% (effect size) absolute non-improvement for those on the swaddled group (i.e. 40% of the subjects will have a non-type 1 or worst hip).

For a two-sided test of 5%, a formula to calculate the sample size is given by

$$N (\text{size per group}) = c * \frac{\pi_1(1 - \pi_1) + \pi_2(1 - \pi_2)}{(\pi_1 - \pi_2)^2}$$

where $c = 7.9$ for 80% power, and $\pi_1=0.2$ and $\pi_2=0.4$

For a 80% power, we have $N (\text{size per group}) = 7.9 * [0.1 (1 - 0.1) + 0.4 (1 - 0.4)]/(0.1-0.4)^2 = 29$

Hence minimum $29 * 2 = 58$ subjects are needed.

In order to increase the statistical power, and assuming at least a 20% dropout, it is decided to include about 40 subjects in each group.

Sampling: There are 6 neonatologists/screeners at post-delivery wards of the hospital who perform the hip ultrasound screening. Out of the 6 neonatologists/screeners, one neonatologist will be assigned as a data collector for the study to reduce a baseline diagnostic bias. On the first days after birth, all newborns of the data collector will be screened using Graf's method of ultrasound according to the Mongolian National Guideline.⁸ After the screening, we will generate a list of all newborns with Graf Type 2a hips on daily basis. All term newborns with Graf Type 2a cases (physiologically immature) will be eligible for the study.

Subject inclusion criteria

Predefined inclusion criteria will be:

1. Term newborns with confirmed Type 2a hips
2. Parents who are able to return for the scheduled follow-up ultrasound examination during the study period
3. Willing to give informed consent
4. Newborns without any symptoms and complaint

Predefined exclusion criteria will be:

1. Newborns with obvious congenital abnormalities (with clear medical consequences)
2. Newborns with needs for intensive care treatment
3. Newborns with low (2499g or less)
4. Newborns with confirmed non-type 2a hips

Randomization sequence will be created using Excel 2007 (Microsoft, Redmond, WA, USA) with a 1:1 allocation using random block sizes of 4 by an independent researcher with no clinical involvement in the trial. After obtaining the consent from the parents, details of the allocated group will be given on colored cards contained in sequentially numbered and sealed envelopes. These will be prepared by the principal investigator and kept in an agreed location on the post-delivery ward. Randomization will take place before discharge when the data collector/neonatologist gives detailed consultation on usual postnatal care of newborns. Corresponding envelopes will be opened

only after the enrolled newborns completed all baseline assessments and it is time to allocate the intervention. Whereas parents allocated to the swaddling group and the research assistants will be aware of the allocated arm, the outcome assessor/radiologist will be kept blinded to the allocation.

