For babies assigned to the “swaddling” group, parents will be instructed to follow a pattern of traditional Mongolian swaddling as described above. For babies assigned to the “non-swaddling” group, parents will be instructed to do not swaddle at all and only use a wide sleeping bag with free leg position.

Trained research assistants will make home visits on weekly basis until the infants are 4-6 weeks of age to check and monitor the compliance of the families by observing the baby during every home visit and collecting retrospectively 24-hour diaries of swaddling and non-swaddling patterns. Also unscheduled visits from monitoring research assistants will be organized to estimate unreported non-compliance conducted for all families 2 to 3 times.

At 4-6 weeks follow up visit, the babies will be checked by Graf’s method of hip ultrasound performed by a trained radiologist uninformed about the initial status of the hips. Regardless of the study group, monthly controls will be fixed until complete maturation to Graf type 1 is documented. Families, who did not show up for follow-up will be contacted by phone or home

visit. In cases when the parents will not be able/willing to come to the follow-up control visit(s), the PI will visit the family and make the follow-up ultrasound examination at their home using a portable ultrasound device (MicroUs EXT-1H, REV:C). All infants in need of therapy (Graf type 2a-, 2c or worse) will be treated with Tubinger orthosis.

Monitoring: In the non-swaddling group, it is expected that some families would not adhere to their instructions of not swaddling because of grandparents/cultural pressures. To monitor compliance and obtain a measure of exposure, multiple sources of information will be used:

1. A retrospective 24-hour history of swaddling/clothing: will be recorded by research assistants during each weekly home visit through recording the carer's descriptions of the style of dress/clothing/ swaddling and length of each during the past 24-hour within the 24-hour retrospective diaries (a kind of behaviour diary adapted to record swaddling/clothing pattern)
2. Direct observation of research assistants during weekly visits: of the dressing/clothing/ swaddling of each child and discreetly recording observations of the type of baby clothing items that each family washed and hung to dry on the day of visit (available for observation during the majority of visits)

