3.5. Statistical analysis

Data will be double computerized using EpiData (The EpiData Association Odense, Denmark) and analyzed using Stata software 9 (Stata Corporation). All ultrasound examination pictures will be uploaded to the HipScreen platform.

Balance checks for the “swaddling” and “non-swaddling” groups will be conducted and reported for all key individual-level variables measured at baseline, including age at hip ultrasound screening in days, gender, risk factors (birth weight ≥ 4000 gr, breech delivery, family DDH history, parity etc.), Graf hip type, alpha angles at baseline and management.

The primary and secondary outcomes will be described as percentage adjusted for the available baseline variables. Outcomes will be evaluated in an intent-to-treat analysis. Univariate analyses will assess factors that will be associated with outcomes and identify potential confounders (with rate ratios of ≥ 2) or variables that differed between study groups at enrollment. These covariates will be included in multivariate analyses. Multivariate logistic regression will be used to estimate the adjusted risks for prevalent outcomes. Pearson's correlation coefficient will be calculated between “non-Type 1” and swaddling days and swaddling hours per day.

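### The sample-size paragraph prints 0.2 where its own figures use 0.1, and its 80% power assumes full adherence although the protocol expects some crossover under intention to treat

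*Protocol*

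**What the plan says.** Protocol section 3.2 gives the non-swaddled rate three times within one paragraph.

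- Prose: "If we assume that 10% of the subjects on the non-swaddled group has a non-Type 1 hip", with 40% in the swaddled group and an absolute difference of 30 points.
- Symbol line: "for 80% power, and $\pi_1=0.2$ and $\pi_2=0.4".
- Arithmetic: "7.9 * [0.1 (1 - 0.1) + 0.4 (1 - 0.4)]/(0.1-0.4)^2 = 29".

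The minimum of 58 infants is then raised, partly for power and partly for loss to follow-up: "assuming at least a 20% dropout, it is decided to include about 40 subjects in each group". The paragraph does not mention adherence.

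Section 3.3, under monitoring, says of the non-swaddling group that "it is expected that some families would not adhere to their instructions of not swaddling because of grandparents/cultural pressures". It gives no rate. Section 3.5 says "Outcomes will be evaluated in an intent-to-treat analysis".

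**The concern.** There are two separate points.

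First, the printed inputs of the formula do not produce the printed sample size. The two values of the non-swaddled rate lead to sizes that differ by a factor of 2.7 (79/29), and the calculation cites no source for either.

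Second, the trial is sized as if every family followed its allocation. An infant in the non-swaddling group who is swaddled is not a dropout. Under intention to treat that infant stays in the non-swaddling denominator and moves its rate towards 40%, so the expected difference is below 30 points. An allowance for dropout restores lost numbers but not a diluted difference. What is at stake is the reading of a non-significant result: section 6 plans recommendations to the public, and the stated 80% would make such a result look more informative than it is.

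**Working it through.** **Inputs from the protocol.** Two-sided 5% test; c = 7.9 for 80% power; rates 0.1 (or, on the symbol line, 0.2) and 0.4; about 40 per group enrolled; dropout of at least 20% (all section 3.2). Crossover is expected but not quantified (section 3.3). The analysis is by intention to treat (section 3.5).

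**Step 1: the protocol's figure.** N = c[p1(1-p1) + p2(1-p2)]/(p1-p2)².

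- 0.1 vs 0.4: 7.9 × (0.09 + 0.24)/0.09 = 28.97, so 29. The printed figure is reproduced.
- 0.2 vs 0.4: 7.9 × (0.16 + 0.24)/0.04 = 79.

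**Step 2: the margin for dropout.** 29/0.8 = 36.25, so 37 per group. Enrolling 40 leaves three to spare. With 20% dropout, 40 × 0.8 = 32 are evaluable.

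**Step 3: power with full adherence.** Exact power of the two-sided 5% chi-square test (summing binomial probabilities over all rejecting tables), 0.1 vs 0.4: 82.8% with 32 per group and 90.1% with 40. The 80% claim therefore holds if adherence is complete.

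**Step 4: power with crossover.** Let a share x of the non-swaddling group be swaddled. The values of x are assumptions.

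- Full risk: these infants carry the 40% risk, so p1 = 0.1 + 0.3x. This is the worst case for dilution from this arm.
- Half the excess risk: p1 = 0.1 + 0.15x. This represents partial or occasional swaddling, and is also an assumption.

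Exact chi-square power against 0.4:

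| x | p1, full risk | 32 per group | 40 per group | p1, half excess | 32 per group | 40 per group |
|---|---|---|---|---|---|---|
| 10% | 0.13 | 71.5% | 80.4% | 0.115 | 77.4% | 85.7% |
| 20% | 0.16 | 59.0% | 67.9% | 0.13 | 71.5% | 80.4% |
| 30% | 0.19 | 46.4% | 54.2% | 0.145 | 65.3% | 74.4% |

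Hand check of one cell (full risk, x = 20%, n = 32) by the normal approximation: 0.24/√[(0.1344 + 0.24)/32] = 2.22; 2.22 - 1.96 = 0.26; power about 60%, against 59.0% exact.

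**Step 5: how much crossover the margin absorbs.** In the full-risk model, with 32 evaluable, power falls below 80% at x of about 1% (pooled normal formula) to 4% (unpooled). With all 40 evaluable the limit is about 9% to 12%.

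**The case against.** A reader might infer from the symbol line that the trial needs 79 per group, or that its power is only 42% (32 evaluable) to 50% (40 evaluable). The protocol does not support this. The 10% in the prose, the 30-point effect and both uses of 0.1 in the arithmetic agree with each other, and 0.2 vs 0.4 would be a 20-point effect. The 29 is not miscalculated.

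A reader might also infer that dropout is the only allowance made, or that 80% power holds only in the most favourable case. That too is stronger than the text allows. Section 3.2 says that the increase to 40 is partly for power, and 40 exceeds 37. Section 3.3 provides telephone contact, home visits and portable ultrasound for families who do not attend, so more than 32 may be evaluable. With all 40, power is still 80% at 10% full-risk crossover.

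Nor is adherence neglected in conduct. Suitable clothing and sleeping bags are supplied, there are weekly and unscheduled visits, and measured exposure feeds a per-protocol analysis. These measures may keep crossover low, but they do not restore the power of the intention-to-treat comparison once it occurs.

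Finally, the crossover rates used here are not the protocol's, and the full-risk model treats occasional swaddling as if it were full swaddling. This stands, and is why the half-excess figures are shown beside it.

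What the objection leaves untouched is that the protocol predicts crossover, chooses the analysis that retains its effect, and states a power that takes no account of it. Since dropout is put at 20% or more, 32 evaluable is a fair planning case.

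**Conclusion.** Both points hold, at modest strength. The symbol line carries a wrong value, almost certainly a slip, with no effect on the 29. The 80% power is correct for 0.1 vs 0.4 with full adherence, but at the planned dropout it survives only about 1-4% full-risk crossover. Over an assumed 10% to 30% crossover, power runs from 72% down to 46% with 32 evaluable and from 80% down to 54% with 40 at full risk. At half the excess risk it runs from 77% to 65% and from 86% to 74%.

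It would be wrong to conclude that the trial has only even odds of detecting its effect. That applies near 30% full-risk crossover, or under the 0.2 reading, which the rest of the paragraph rules out. Nor does the protocol say that it would read a null result as proof of safety. The risk is that the stated power invites others to do so.

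**What to change.** In section 3.2:

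1. Print 0.1 for the non-swaddled rate on the symbol line, so that it agrees with the prose and the arithmetic.
2. Replace the unqualified 80% by the intention-to-treat power of the fixed 40 per group, for 32 to 40 evaluable, over a stated range of crossover in the non-swaddling group. Give the risk assumed for infants who cross over.
3. State that a non-significant result does not rule out harm smaller than 30 points.

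This rewords one paragraph. Enrolment, procedures and the analysis stay as they are. The cost is a less favourable stated power.

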3.3. Data collection and quality control

After a routine standard physical examination on the first day of life, all newborns will be examined by hip ultrasound. The standardized and uniform system of Graf will be used for diagnostics.²² The hip ultrasound examination will be performed by a trained and experienced neonatologist using an ultrasound machines (GE Logiq series) with a linear array transducer operating on an ultrasound frequency of 7–10 MHz. A Sonofirst® holding cradle and transducer fixation unit (Orthopunkt, Solothurn) will be used to prevent tilting errors and to standardize examination techniques.^{14,22} A web-based, password-protected tool, “HipScreen” (WebWaren, Bern, Switzerland)¹⁴ will be used for quality control purpose. The tool enables the screener to upload DICOM files exported from the ultrasound machines. Four images (two per hip side; one of them with measured alpha and beta angles according to Graf), will be required. This will allow continuous and reliable review of hip grading, diagnosis of DDH, and treatment decisions. Trained, on-site experts will check all examinations and promptly send comments to the screener. Discrepancies between expert assessments will be resolved by discussion and consensus.

After identification of all term newborns with Graf Type 2a cases (physiologically immature) of the neonatologist/data collector will be listed and the newborns and their mothers will be undergoing the screening process by research assistants to see whether they meet the inclusion criteria. The parents of the physiologically immature cases will be given oral information about hip dysplasia and study purpose. Consequently, parents will give their oral consent to participate. Those who refuse consent will be registered, but will not be included.

After the randomization of eligible newborns with physiologically immature (Graf Type 2a) hips, the research assistants will explain and give detailed information about the study again to the parents in both “swaddled” and “non-swaddled” groups. The parents will be requested to sign an informed consent form if they agree to take part in the study before they are given an ID number. After the obtaining the written consent form, a brief questionnaire about demographic (e.g. birth date, gender of newborn etc.) and birth related information such as fetal position, birth weight, number of parity and family history of DDH will be filled by the research assistants.

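### The randomization section names one fixed block size, 4, in the protocol itself, so unblinded staff who track earlier envelopes could deduce up to a third of assignments

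*Protocol*

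**What the plan says.** All references are to the Protocol.

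- **Sequence.** Section 3.2 has the list created "with a 1:1 allocation using random block sizes of 4 by an independent researcher", who has no clinical role in the trial. No stratification factor is stated.
- **Setting.** Section 3.2 names a single centre: "The National Center for Maternal and Child Health (NCMCH) is purposely selected as a study site". Of its screeners, "one neonatologist will be assigned as a data collector for the study to reduce a baseline diagnostic bias".
- **Concealment.** Section 3.2: "details of the allocated group will be given on colored cards contained in sequentially numbered and sealed envelopes". It continues: "These will be prepared by the principal investigator and kept in an agreed location on the post-delivery ward". An envelope is opened only after baseline assessments are complete.
- **Timing.** Section 3.2: "Randomization will take place before discharge when the data collector/neonatologist gives detailed consultation on usual postnatal care of newborns".
- **Who screens.** In Section 3.3 the listed Type 2a newborns and their mothers "will be undergoing the screening process by research assistants to see whether they meet the inclusion criteria".
- **Who knows the arm.** Section 3.2: "Whereas parents allocated to the swaddling group and the research assistants will be aware of the allocated arm, the outcome assessor/radiologist will be kept blinded".
- **Consent.** Section 3.2 places parental consent before the allocation is given. Section 3.3 describes oral consent first. After randomization the research assistants explain the study again, and only then do parents sign.

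**The concern.** The wording describes the block sizes as random but gives only one. It may have been meant as randomly permuted blocks of size 4. The consequence is the same: the order inside a block is random, but its length is fixed and disclosed.

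A sealed envelope hides the next card. It does not hide what the earlier cards imply when the block length is known. With one list at one site, the earlier cards form a single series that is easy to follow. The protocol does not separate the research assistants who screen and explain the study from those who know the arm.

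If the coming arm can be anticipated, encouragement to join may come to depend on it. So may judgements on softer entry criteria, such as whether parents are able to return for follow-up. The protocol states its expectation that swaddling is harmful (Sections 2 and 6), so staff are not indifferent to the arm. With 40 infants per arm, each infant moves that arm's event rate by 1/40 = 2.5 percentage points.

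**Working it through.** The plan gives no predictability figure to reproduce, so it is derived here.

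**Inputs.** Allocation 1:1 and block size 4 (Section 3.2, randomization). One unstratified list (one site, no strata stated). About 40 per group, so 80 infants = 20 blocks (Section 3.2, sample size). Assumed observer: knows the block size and has tracked every earlier allocation without error.

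**Assignments known with certainty, block of 4.** There are 6 equally likely orders of AABB.
- The 4th place is always forced: 1.
- The 3rd place is forced when the first two match, with probability 1/3.
- Expected forced per block = 1 + 1/3 = 4/3. Share = (4/3)/4 = 33.3%.
- Over 20 blocks: 20 × 4/3 = 26.7 of 80. The number is 20 + Binomial(20, 1/3), so at least 20, with a 95% range of 23 to 31.

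**Best-guess accuracy, block of 4.** The observer guesses the arm that is behind and tosses a coin when the arms are level.
- 1st place: 1/2.
- 2nd place: 2/3.
- 3rd place: (1/3 × 1) + (2/3 × 1/2) = 2/3.
- 4th place: 1.
- Sum = 17/6 per block. Share = (17/6)/4 = 70.8%, or 56.7 of 80, against 40 of 80 by chance.

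**Alternatives.** The fixed sizes were enumerated in the same way. The varying sizes were simulated (500 lists of 80, sizes equally likely) with an observer who knows which sizes are possible, but not their order, and updates on every past allocation.

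| Block scheme | Known with certainty | Best guess correct |
|---|---|---|
| Fixed 4 (as written) | 33.3% | 70.8% |
| Fixed 6, known | 25% | 68.3% |
| Fixed 8, known | 20% | 66.6% |
| Varying 4/6 | about 5% | about 69% |
| Varying 2/4/6 | about 4% | about 70% |
| Varying 4/6/8 | about 2% | about 68% |

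Varying the size removes nearly all certain predictions: with 4/6/8, about 0.02 × 80, or roughly 2 infants, instead of 27. It removes little of the guessing advantage, because any blocked list tends to return to balance.

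**The case against.** Permuted blocks of 4 with an independent list generator and sequentially numbered sealed envelopes are a common design. The protocol also has real safeguards, and some stronger readings go beyond its text.

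- **The neonatologist sees every allocation.** A reader might infer this because randomization takes place at that consultation. The protocol does not say who opens the envelope, and among staff it names only the research assistants as aware of the arm. The route that the text supports runs through them, and they do not measure the alpha angle.
- **The angle could be shaded near 50° or 60° to suit the coming arm.** This is much less likely. Section 3.3 requires four uploaded images per infant and a holding cradle with transducer fixation, and experts check all examinations. Section 3.2 requires confirmed Type 2a hips. The scan is done on the first day of life and randomization happens later, before discharge, from a daily list. Several infants may be waiting, so the envelope an infant will receive is often not settled when the angle is measured.
- **Baseline alpha is the main predictor of outcome, so the primary comparison is biased.** The protocol does not say this. Section 3.5 lists baseline alpha among the variables checked for balance and puts variables that differ between groups into the multivariable model. That partly handles measured imbalance.
- **A third of assignments are simply known in advance.** The third is an expected maximum for a perfect observer. The protocol does not say that ward staff hold the block size; that is inferred from its being printed there.

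These points stand, but they do not dispose of the concern. Image review does not govern encouragement or softer eligibility judgements. Refusals are registered, which leaves a trace of selective consent but does not prevent it. Covariate adjustment cannot correct unmeasured selection such as parental motivation. Blinding the outcome assessor protects measurement, not enrolment.

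**Conclusion.** The point holds as a moderate weakness in allocation concealment that is cheap to reduce. The text fixes and discloses one block size while calling it random, and it places unblinded staff at the point where eligibility and consent are settled. Up to one third of assignments (about 27 of 80) could be deduced, and 71% guessed correctly.

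This rests on two assumptions: that someone at the consent stage knows the size, and that the same person follows the earlier envelopes. Both are made possible by the protocol; neither is stated as fact. The figures measure predictability. They are not an estimate of bias in the treatment comparison, and nothing in the document shows that bias would occur.

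The consent order matters alongside this. If the written signature follows randomization, as Section 3.3 describes, the arm is already known at signature for every infant, whatever the block size. Section 3.2 may mean only the oral consent, but it does not say so.

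**What to change.** 1. Have the independent researcher generate the list with randomly varying permuted blocks, for example 4, 6 and 8.
2. Withhold the sizes from ward and research staff, and remove the block size from the protocol they use. A restricted document held by the independent researcher can record it. Whoever fills the envelopes sees the sequence, so it would be consistent for the independent researcher to fill them too, rather than the principal investigator.
3. Reconcile Sections 3.2 and 3.3 so that eligibility is decided and written consent signed before the envelope is opened. This is needed because step 1 leaves best-guess accuracy at about 68%.

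**Cost.** Step 1 takes minutes for the person already making the list. Its downside is that the final arm sizes may differ by up to 4 infants, if enrolment stops halfway through a block of 8. Steps 2 and 3 are changes of wording and of the order of work on the ward, and need no extra infants.
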